As time permits during the screening visit and after consenting, baseline characterization measures will also be collected. Participants may be scheduled for an additional visit and the necessary additional time to complete these assessments prior to beginning the 10-day rTMS treatment session. Following this, subjetes will have 8 follow-up visits [at the end of continued rTMS treatment phase, at rTMS follow-up visit #2, #4, #8, #12, and once a month during no rTMS follow-up phase].

Characterization measures include:

- Hamilton Anxiety Scale (HARS): A 21-item self-report inventory, which assesses the severity of anxiety. Completion time: ~ 5 minutes.
- Montgomery-Asberg Depression Rating Scale (MADRS): A clinical assessment to identify symptoms of depression. This assessment is especially useful in identifying changes in depression symptoms over time. Completion time: < 10 minutes.
- Positive and Negative Affect Scale (PANAS): A self-report scale to assess state-level affect. Completion time: < 5 Minutes.
- Profile of Mood States (POMS): A questionnaire designed to measure present mood state by a list of adjectives on a 5-point Likert scale and measures six dimensions of affect, including tension-anxiety, depression-dejection, anger-hostility, vigor-activity, fatigue-inertia, and confusion-bewilderment. The measure has been shown to produce reliable and valid profiles of mood state. Completion time: ~ 5 minutes.
- Snaith-Hamilton Pleasure Scale (SHAPS): A 14-item self-report scale designed to measure hedonic-tone/anhedonia. Completion time: ~ 5 minutes.
- Temporal Experience of pleasure Scale (TEPS): A 20-item self-report scale designed to evaluate individual trait dispositions in anticipatory and consummatory pleasure experiences. Completion time: ~ 15 minutes.

- Quality of Life Enjoyment and Satisfaction Questionnaire Short Form (Q-LES-Q-SF): A self-report scale designed to measure social ties between the participants and their friend, family, co-workers, etc. Completion time: ~ 15 minutes.
- Time-line follow back (TLFB). The TLFB will be used to assess substance use behavior. This assessment will be either self-administered or administered by one of the investigators. Participants will read the instructions and/or will be guided by the therapist or investigator in filling out the calendar. A lifetime TLFB will be administered at baseline and during each visit.
- Columbia-Suicide Severity Rating Scale (C-SSRS):to assess suicidality ideation.

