If subjects are unable or unwilling to attend these visits, they will be contacted by phone or email, and an attempt will be made to obtain measures in this manner.

F. Objectives

Primary: The primary goal of the current study is to investigate the effects of repetitive transcranial magnetic stimulation (rTMS) targeting the left DLPFC on cocaine craving. The co-primary goal is to investigate rTMS effect on cocaine consumption.

Secondary: Our secondary goals are to evaluate rTMS effects on: (1) mood; (2) cognitive functions.

Exploratory: Our exploratory goals are evaluating rTMS effects on: (1) BOLD response in DLPFC during tasks known to activate this area; (2) resting state functional connectivity between the DLPFC and nodes of the executive control networks.

Outcomes measures: Our primary outcomes will be: (1) change in craving score as measured by the CCQ from pre- to post treatment [baseline and after rTMS treatment: 2 weeks, 3 months, 6 months]; (2) changes in cocaine consumption as measured by TLFB self-reports and urine drug screen from pre- to post treatment [baseline and after rTMS treatment: 2 weeks, 3 months, 6 months]. Our secondary outcomes are: Changes in the scores on the 90

Symptoms Questionnaire (SCL-90) from pre- to post treatment [baseline and after rTMS treatment: 2 weeks, 3 months, 6 months]; (2) changes in the scores of the Montgomery-Asberg Depression Scale (MADRS) from pre- to post treatment [baseline and after rTMS treatment: 2 weeks, 3 months, 6 months]; (3) changes in the scores on the Hamilton Anxiety Rating Scale (HARS); (4) changes in the scores on the frontal assessment battery (FAB), and on the Flanker task from pre- to post treatment [baseline and after rTMS treatment: 2 weeks, 3 months, 6 months];

(5) changes in the scores of the Iowa Gambling Task from pre- to post treatment [baseline and after rTMS treatment: 2 weeks, 3 months, 6 months];

In addition, in order to investigate DLPFC engagement by TMS, the following exploratory outcomes will be analyzed: (1) DLPFC BOLD signal change in response to cocaine-related stimuli from baseline to each time point [baseline and after rTMS treatment: 2 weeks, 3 months]. (2) Change in resting state functional connectivity, from baseline to each time point (z-score) [baseline and after rTMS treatment: 2 weeks, 3 months].

1. Aims

Primary aim:

To determine the effects of rTMS on cocaine craving and consumption in patients with CUD.

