- Changes in CCQ score between the active rTMS and sham group, and from pre- to post treatment [baseline and after rTMS treatment: 2 weeks, 3 months, 6 months];
- Percent of negative urine samples between the active rTMS and sham group, and from pre- to post treatment [baseline and after rTMS treatment: 2 weeks, 3 months, 6 months].

Secondary aims:

- Changes in the scores on the 90 Symptoms Questionnaire (SCL-90) from pre- to post treatment [baseline and after rTMS treatment: 2 weeks, 3 months, 6 months];
- Changes in the scores of the Montgomery-Asberg Depression Scale (MADRS) from pre- to post treatment [baseline and after rTMS treatment: 2 weeks, 3 months, 6 months];
- Changes in the scores on the Hamilton Anxiety Rating Scale (HARS);

- Changes in the scores on the frontal assessment battery (FAB), and on the Flanker task from pre- to post treatment [baseline and after rTMS treatment: 2 weeks, 3 months, 6 months];
- Changes in the scores of the Iowa Gambling Task from pre- to post treatment [baseline and after rTMS treatment: 2 weeks, 3 months, 6 months];

Exploratory aims:

- DLPFC BOLD signal change in response to cocaine-related cues from baseline to each time point, and between the active and sham group;
- Changes in resting state functional connnectivity between the DLPFC and other nodes of the executive control network (ECN), from baseline to each time point, and between the active and sham group.

Statistical Analysis

Behavioral measures on each of the cognitive tasks as well as questionnaire data from each of the experimental conditions will be compared both within and between experimental groups using mixed, repeated-measures ANOVA, and linear mixed models. When assessing the statistical results from the behavioral and questionnaire data, a standard α -level of 0.05 will be used. Alpha-levels for multiple comparison follow-up tests will be corrected using an appropriate method (e.g., Bonferroni, Tukey, Scheffe).

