The imaging data will be pre-processed and analyzed with MatLab. All functional images will be directly registered upon high resolution MPRAGE anatomical scans obtained during the same imaging session. Location and intensity of activations from individual and/or grouped data will be translated into 3D stereotaxic coordinates. Functional images of activation-induced BOLD signal changes will be determined using cross correlation or multiple regression analyses. Differences in structural and functional measures between active rTMS and sham participants will be assessed using between group comparisons (e.g., independent samples t-tests). Correlation and multiple regression approaches will be used to test for an association between clinical assessment measures and task-specific neural

measures (e.g., correlation between cocaine craving scores and neural activation in the striatum).

Real vs Sham rTMS Power Analysis. Because no sham-controlled studies have been performed assessing the chronic effects of rTMS administration on behavioral or neurophysiological measures in patients with CUD, anticipating an effect size is difficult. However, open label studies have shown substantial behavioral changes in clinical populations and could have similar effects in reducing cocaine use. In order to capture a reliable effect while not committing a type II error, a medium-large effect size (Cohen's d = 0.65) will be used to calculate the necessary participants to compare real and sham iTBS treatments. Approximately 30 participants per group will be required to detect significant differences between these two independent groups at a nominal α level of 0.05 in a one-tailed t-test assuming a medium-large effect size. We anticipate approximately 80-85% retention rate at visit 24, based on previous studies conducted in similar patient populations by our group. Therefore, 80 participants will be recruited at baseline, 40 for real and 40 for sham iTBS, to acquire the necessary 30 participants in each group for analysis.

G. Data Management and Safety measures

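### The TLFB is a lifetime recall repeated at every visit, with no pre-treatment window matched to the follow-up windows, although it feeds a pre-to-post co-primary outcome

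*Combined protocol and SAP*

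**What the plan says.** Section F (Objectives, Outcomes measures) and the synopsis give the second primary outcome as "changes in cocaine consumption as measured by TLFB self-reports and urine drug screen from pre- to post treatment", assessed at "baseline and after rTMS treatment: 2 weeks, 3 months, 6 months".

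The instrument is described only in section D, in the list of characterization measures. Its purpose is given in one line: "The TLFB will be used to assess substance use behavior". Participants complete it alone or are "guided by the therapist or investigator in filling out the calendar". The recall period is set by "A lifetime TLFB will be administered at baseline and during each visit". The same section schedules 8 follow-up visits.

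The Aims list a different measure of consumption: "Percent of negative urine samples between the active rTMS and sham group, and from pre- to post treatment". They do not mention the TLFB. The Statistical Analysis section says that task and questionnaire data will be "compared both within and between experimental groups using mixed, repeated-measures ANOVA, and linear mixed models". It names no TLFB variable.

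**The concern.** A change in consumption is a change in rate: use over some period before treatment against use over a comparable period after it. A lifetime recall has no such period. Its total accumulates, so later values carry all earlier use, and the amount added depends on how long ago baseline was. The plan gives no look-back length, no unit (days, grams, percent of days) and no derived variable that would turn the recall into a rate.

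Two things are at stake. First, if totals are what the form yields, the self-report half of a co-primary outcome would not measure the pre-to-post change that the plan names, and recall error over a whole history would enter an outcome spanning 2 weeks to 6 months. Second, if the calendars do hold daily entries, the choice of window stays open until the data are in hand, and several plausible windows could be tried.

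**Working it through.** **The plan's own figure.** The documents give no number for the TLFB. The only related figure is the sample size of 30 per group, from d = 0.65 and a one-tailed test at 0.05. Power is not stated; 80% is assumed here.

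n = 2(1.645 + 0.842)² / 0.65² = 2 × 6.185 / 0.4225 = 29.3, rounded up to 30. The noncentral t calculation gives 29.97, also 30. The figure reproduces, and nothing below changes it.

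**What a lifetime total can do.** Let L0 be the true number of lifetime use days at baseline and U(t) the use days from baseline to time t, with U(t) ≥ 0.

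- True change: L(t) − L0 = U(t). It is never negative, and it is zero only if there is no use after baseline. L0 cancels, so pre-treatment use does not enter the change at all.
- Reported change, with recall errors e0 and e(t): D(t) = U(t) + [e(t) − e0]. If the errors are unrelated to U(t), Var D(t) = Var U(t) + Var[e(t) − e0].
- The reported change can therefore move either way, but a fall would reflect recall disagreement and not reduced use. The documents give nothing on the size of e(t) − e0.

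**Illustration.** The rates are assumed, because the plan gives none: 12 use days per 28 (3 per week) before treatment, then 12, 6 or 0 per 28 (3, 1.5 or 0 per week). Times are counted from the start of treatment as weeks 2, 14 and 26, from the 2-week treatment phase and the two 12-week follow-up phases. Recall is taken as perfect.

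| Use after baseline | Lifetime change, week 2 | Week 14 | Week 26 | 28-day window change, weeks 14 and 26 |
|---|---|---|---|---|
| Unchanged (12 per 28) | 3 × 2 = +6 | 3 × 14 = +42 | 3 × 26 = +78 | 12 − 12 = 0 |
| Halved (6 per 28) | 1.5 × 2 = +3 | 1.5 × 14 = +21 | 1.5 × 26 = +39 | 6 − 12 = −6 |
| Stopped (0 per 28) | 0 | 0 | 0 | 0 − 12 = −12 |

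The lifetime columns are the same for baseline totals of 200, 1000 and 3000 days. Three points follow.

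1. The lifetime change shows no reduction for anyone, including the participant who stops. The windowed change has the right sign and size.
2. With unchanged behaviour the lifetime change runs +6, +42, +78. A within-group repeated-measures analysis of it would show an effect of time that is only elapsed time.
3. Between arms the contrast survives. If one arm halves use and the other does not change, week 26 gives 39 against 78, a difference of 39 days of use since baseline.

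**The 2-week point.** Only about 14 days have passed, so a 28-day window ending there would take in about 28 − 14 = 14 pre-treatment days. A 14-day window does not overlap. At the assumed rates it holds 12 × 14/28 = 6 use days before treatment, and 6, 3 or 0 after.

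**The entry criterion.** Inclusion criterion 3 in section C requires at least 48 hours without cocaine. A 14-day baseline window that contains those 2 days has only 12 days on which use can occur: 12 × 12/28 = 5.1 use days instead of 6. This affects both arms alike, but it biases the pre-to-post change.

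**The case against.** The strongest reply is that lifetime describes how far back the calendar reaches, not the endpoint. Nowhere does the plan say that lifetime totals will be computed or subtracted. The TLFB is filled in as a calendar. If its entries are dated by day, the baseline calendar already contains the weeks before treatment and later ones contain the weeks since, so matched windows could be derived without new data. That stands. A reader might infer that the measure can only rise, or that it cannot show a pre-to-post reduction. The documents do not support either: the true total is flat under abstinence, reported totals can fall through recall error, and dated entries would allow a rate. What the reply leaves unanswered is that the plan states neither the resolution of the entries nor which window counts.

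Two further replies also stand. Randomised arms can be compared on use since baseline, so the test of active against sham is not defeated; but that is not the pre-to-post change that the plan names, and by itself it does not use the baseline rate. And the urine measure, the only consumption measure in the Aims, does not depend on the TLFB, so the point covers only the self-report half of the co-primary outcome.

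A reader might also infer a definite loss of power from recall error. The documents give neither a distribution of use days nor a spread for recall disagreement, so no such figure can be supported.

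**Conclusion.** The point holds in a limited form. The plan prescribes a repeated lifetime recall for a co-primary outcome defined as change, and it names no matched windows and no summary variable. A valid pre-to-post change in self-reported use then depends on whether dated daily entries happen to be kept and on a window chosen later.

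The direction of the problem follows from arithmetic alone: the change in a true lifetime total equals use since baseline and cannot be negative. Its size in the illustration (+39 and 0 days at week 26, where a 28-day window gives −6 and −12) rests on assumed rates and perfect recall. Sample size, the urine outcome and the between-arm comparison of use since baseline are not undermined. The plan should be changed, because the better method costs almost nothing, but the point does not invalidate the trial.

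**What to change.** - Administer the lifetime TLFB once, at baseline, for description only.
- For the outcome, record dated daily use for a fixed pre-treatment window and, at each visit, for the days since the last visit. State on the form that entries are by day.
- Name one variable, for example percent days of use, and analyse it over windows of equal length before baseline and before each of 2 weeks, 3 months and 6 months, adjusted for the baseline window.
- Use no more than about 14 days for the 2-week comparison. A longer window may serve the two later points if the baseline window used with it has the same length. Collecting 28 pre-treatment days would cover both.
- Say where the baseline window ends in relation to the required 48 hours of abstinence.
- State in the Aims and in the Statistical Analysis section how the TLFB variable stands beside percent negative urine samples.

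The cost is a change to protocol and form wording. Follow-up visits lose a lifetime recall, and the sample size does not change. If data collection has begun, first check whether completed calendars carry daily dates. If they do, the windows can be fixed in writing before unblinding and derived from what is already held.

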On the basis of these findings, the aim of this study is to test whether rTMS of the left DLPFC could be effective in treating CUD.

C. Study Overview

This is a between-subject double-blind, randomized, sham-controlled study with a 1:1 allocation into two parallel arms: 15 Hz, or sham rTMS stimulation. Participants will be 80

treatment-seeking patients, between the ages of 18-65, who meet diagnostic criteria for CUD (moderate to severe). Criteria for study enrollment are listed below. All participants will be informed about study procedures and will provide written informed consent prior to the experiment, in line with the Helsinki Declaration developed by the World Medical Association.

Recruitment: We aimed to recruit patients from rural and urban areas, in order to take account of possible differences in substance consumption and addiction severity. Therefore, recruitment will take place in two different cities: Rome, a large metropolitan area, and Chieti, a small city in the center of Italy, where the majority of patients will be enrolled from rural surroundings. Participants enrollment will be performed by a multidisciplinary team (physicians, psychologists), who have been trained and have extensive experience in performing the assessments included in the current study.

Inclusion criteria

- 1. Age 18 65;
- 2. Current diagnosis of cocaine use disorder (from moderate to severe), based on the Diagnostic and Statistical Manual of Mental Disorder Fifth Edition (DSM-5);
- 3. Abstinence from cocaine for at least 48 hrs.

Exclusion criteria

- Current DSM-5 diagnosis of substance use disorders other than nicotine Current DSM-V diagnosis of moderate to severe alcohol use disorders
- 2. Current DSM-5 diagnosis of schizophrenia, bipolar disorder, or other psychotic disorder;
- 3. Use in the past 4 weeks of any medication with known proconvulsant action; or current regular use of any psychotropic medications (benzodiazepines, antipsychotic medications, tricyclic antidepressants, anti-epileptics, mood stabilizers);
- 4. Any history of any clinically significant neurological disorder, including organic brain disease, epilepsy, stroke, brain lesions, multiple sclerosis, previous neurosurgery, or personal history of head trauma that resulted in loss of consciousness for > 5 minutes and retrograde amnesia for > 30 minutes;

- 5. Any personal or family history (1st degree relatives) of seizures other than febrile childhood seizures;

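### Baseline cocaine use is collected by TLFB but is not named as a covariate for the consumption co-primary; adding it is a free gain in precision of uncertain size

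*Combined protocol and SAP*

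**What the plan says.** The consumption co-primary is described in two ways. Under F. Objectives, Outcomes measures (and in the synopsis) it is "changes in cocaine consumption as measured by TLFB self-reports and urine drug screen from pre- to post treatment". Under 1. Aims, Primary aim, it is "Percent of negative urine samples between the active rTMS and sham group, and from pre- to post treatment". Both are to be assessed at baseline, 2 weeks, 3 months and 6 months.

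On baseline data, the characterization measures in D. Procedures say of the calendar interview: "A lifetime TLFB will be administered at baseline and during each visit".

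The Statistical Analysis section names mixed repeated-measures ANOVA and linear mixed models for cognitive-task and questionnaire data. It names no covariate and does not mention urine results. The Power Analysis paragraph states that "a medium-large effect size (Cohen's d = 0.65) will be used to calculate the necessary participants" and that "Approximately 30 participants per group will be required to detect significant differences between these two independent groups", with the test taken "at a nominal α level of 0.05 in a one-tailed t-test assuming a medium-large effect size". That calculation compares two independent groups without adjustment. It does not assign the effect size to either co-primary, or say whether the standard deviation is that of the follow-up value or of the change.

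**The concern.** Use before treatment is a natural candidate to predict use afterwards. The plan schedules that information for every participant but gives it no stated role in the active-versus-sham comparison beyond the phrase pre to post. If the comparison is made on a change, the error in the pre-treatment value is carried into the outcome. If it is made on follow-up alone, the between-person variance that baseline could explain stays in the error term.

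The urine measure is the weaker one at baseline. The listed drug screen belongs to stimulation days (D. Procedures, rTMS), no set of pre-treatment samples is defined from which a percentage could be formed, and entry requires at least 48 hours of abstinence. A TLFB window is a fuller pre-treatment measure.

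At stake is power on a co-primary in a trial sized to 30 analysable participants per arm. Because the plan is silent, the handling of baseline could also be chosen after the data are seen.

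**Working it through.** **Inputs from the Power Analysis paragraph.** d = 0.65; alpha 0.05, one-tailed; 30 analysable per arm; 40 per arm recruited; retention 80-85%, so 0.80 × 40 = 32 to 0.85 × 40 = 34 completers per arm.

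**Assumed, not in the documents.** Power of 80%; correlation rho between the baseline measure and the follow-up outcome; d in units of the follow-up SD; continuous outcome and linear model; equal SDs before and after for the change-score comparison.

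**1. The plan's own figure.** n per arm = 2 × (1.645 + 0.842)² / 0.65² = 12.37 / 0.4225 = 29.3, so 30. With the noncentral t (58 df, noncentrality 0.65 × √15 = 2.517), power at 30 per arm is 80.0% one-tailed. The stated 30 is reproduced. The same comparison two-sided has 69.7%.

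**2. Formulas.** Noncentrality = δ × √(n/2), where δ is:
- unadjusted follow-up comparison: 0.65;
- baseline as covariate: 0.65 / √(1 − rho²), with one degree of freedom lost;
- change score on the same measure: 0.65 / √(2(1 − rho)).

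At rho 0.5 the covariate gives δ = 0.65 / √0.75 = 0.751 and noncentrality 2.907. The change score gives δ = 0.65 / √1 = 0.65, the same as the unadjusted comparison.

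**3. Power, one-tailed 0.05, 30 per arm.**

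| rho | Unadjusted follow-up | Change score | Covariate | Gain over unadjusted | Gain over change |
|---|---|---|---|---|---|
| 0.3 | 80.0% | 67.6% | 83.2% | 3.2 | 15.6 |
| 0.5 | 80.0% | 80.0% | 89.0% | 9.0 | 9.0 |
| 0.7 | 80.0% | 94.1% | 96.7% | 16.7 | 2.6 |

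The two gains move in opposite directions as rho rises and agree only at 0.5, so any quoted gain needs its comparator.

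**4. Two-sided 0.05, 30 per arm, rho 0.5.** 69.7% to 81.5%, a gain of 11.8 points.

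**5. At the expected number of completers, one-tailed, rho 0.5.** 32 per arm: 82.3% to 90.7%, a gain of 8.4 points. 34 per arm: 84.3% to 92.2%, a gain of 7.9 points.

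**Limits.** The change-score column supposes the same measure before and after. Baseline TLFB days and percent of negative urines are different measures, and their correlation is a separate unknown. The factor 1 − rho² belongs to a linear model and does not carry over directly to a binomial model on the logit scale.

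**The case against.** A reader might infer that the plan subtracts a baseline urine value. It does not say so. The Primary aim bullet for CCQ speaks of changes; the urine bullet beside it speaks of a percentage compared between arms and over time. Change in the Outcomes measures text can be read as naming an outcome rather than a model. The plan also names linear mixed models, and one with a common baseline mean would be about as efficient as covariate adjustment. This stands: the supportable statement is that baseline handling is unspecified, not that an inefficient change score has been chosen. It does not remove the point, because the sentence naming those models does not cover urine results and no covariate appears anywhere.

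A reader might also take the 12-point gain as the headline. It holds only for a two-sided test at rho 0.5 and 30 per arm; on the plan's one-tailed basis the figure is 9 points, or about 8 at the expected completers.

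A third inference is that leaving out the covariate biases the trial. In a randomised 1:1 comparison it does not, nor does it inflate the type I error; chance imbalance is already allowed for in the error rate.

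Finally, the Recruitment text under C. Study Overview, "in order to take account of possible differences in substance consumption and addiction severity", explains why two cities were chosen. It does not establish that baseline use predicts outcome, so it cannot support any particular rho. It is also fair to say that the more basic gap is the lack of a clearly specified model for the urine endpoint. The covariate belongs in the sentence that fills that gap.

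**Conclusion.** The point holds as an efficiency improvement. The consumption co-primary has no named baseline covariate, the sample size is unadjusted, the role of baseline in the urine comparison is otherwise unspecified, and a suitable pre-treatment measure is already scheduled.

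The size is uncertain. One-tailed with 30 per arm, the illustrative gain over an unadjusted follow-up comparison runs from about 3 points (rho 0.3) to about 17 (rho 0.7). Over a same-measure change score it runs from about 16 points down to about 3. These figures rest on an assumed rho, a continuous outcome, a linear model, and an effect size that the plan does not tie to this endpoint. They show the order of the gain and are not a power statement for percent of negative urines. If rho is near zero, almost nothing is gained and one degree of freedom is spent.

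**What to change.** State in the Statistical Analysis section that, for the between-arm comparison of consumption at each stated time point, the follow-up value is modelled with arm as the effect and baseline TLFB cocaine-use days as a covariate, in place of analysing a pre-to-post change. The follow-up value would be negative urines out of samples due (for example, a binomial GEE or mixed model) and, if kept, TLFB use days. Fix the length of the pre-treatment window in advance; the sponsor should choose it (4 weeks is one example). State the scale on which the arm effect is reported.

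The plan collects characterization measures as time permits, with an extra visit allowed, so it should also say that the baseline TLFB must be complete before the first stimulation session.

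The cost is SAP wording and one degree of freedom. No new assessments or participants are needed.

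### The plan does not say which model term decides the craving outcome; if either the arm effect or the arm-by-time interaction may count as success, the false-positive rate is about 9.75%, not 5%

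*Combined protocol and SAP*

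**What the plan says.** The craving primary is defined under Outcomes measures, in the synopsis and again in section F, as "change in craving score as measured by the CCQ from pre- to post treatment [baseline and after rTMS treatment: 2 weeks, 3 months, 6 months". The Primary aim restates it as "Changes in CCQ score between the active rTMS and sham group, and from pre- to post treatment". Three post-baseline times are listed and none is ranked above the others.

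The Statistical Analysis section gives one sentence of method for all behavioural and questionnaire data: they "will be compared both within and between experimental groups using mixed, repeated-measures ANOVA, and linear mixed models". On error control it adds that "a standard α -level of 0.05 will be used" and that "Alpha-levels for multiple comparison follow-up tests will be corrected using an appropriate method (e.g., Bonferroni, Tukey, Scheffe").

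The power paragraph that follows sizes the trial to "detect significant differences between these two independent groups at a nominal α level of 0.05 in a one-tailed t-test". It names no visit and no model.

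**The concern.** A mixed ANOVA of CCQ by arm and time produces two omnibus tests that involve the arm, and they answer different questions. With baseline as a level of time, the arm main effect averages in a visit at which treatment cannot yet have acted, so it tests a diluted difference. The interaction tests any difference in profile, on 3 df. If change from baseline is the response instead, the arm effect becomes the treatment test and the interaction asks only whether the effect varies between visits. The deciding term therefore depends on how baseline is handled, which the plan leaves open.

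The stated correction applies to follow-up comparisons, not to these two tests. The same CCQ data could be positive on one term and negative on the other, with the choice made after the results are seen. This is the first-listed primary outcome of a small trial.

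**Working it through.** **Inputs from the document.** Two arms, 1:1 (Study Overview); baseline plus three later times (Outcomes measures); d = 0.65, one-tailed 0.05, 30 per group needed and 40 per group recruited (power paragraph).

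**Assumed.** SD of 1 at each visit, equal correlation ρ of 0.3, 0.5 or 0.7 between any two visits, complete data, and 80% power for the plan's own calculation (no power is stated). Steps 2 and 3 take baseline as a level of time unless noted.

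**1. The plan's own figure.** n = 2(1.645 + 0.842)²/0.65² = 29.3, so 30 per group; exact one-tailed t-test power is 80.0%. The figure is reproduced. It belongs to a single two-group comparison at an unnamed visit, so it does not identify either ANOVA term. ANOVA F tests have no direction; the same t-test run two-sided at 30 per group has about 70% power.

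**2. No true effect.** With equal correlations the two tests use separate error terms and are independent:
- P(at least one significant) = 1 − 0.95² = 9.75%
- P(exactly one significant) = 2 × 0.05 × 0.95 = 9.5%

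Simulation, including serially decaying (AR(1)) correlations, gave 9.1–9.7% with Greenhouse-Geisser correction and 9.5–11.1% without. Using change scores instead, it gave 9.2–9.8% with the correction.

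**3. Constant true effect, d = 0.65 at all three later visits.**
- Arm main effect: noncentrality = (3d/4)/√[(2/n)(1 + 3ρ)/4]. At n = 30, ρ = 0.5: 0.4875/0.204 = 2.39 on 58 df, power 65%.
- Interaction: λ = (n/2)(3d²/4)/(1 − ρ) = 15 × 0.317/0.5 = 9.51 on 3 and 174 df, power 73%.
- Disagreement: 0.651 × 0.273 + 0.727 × 0.349 = 43.1%.

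| | ρ = 0.3 | ρ = 0.5 | ρ = 0.7 |
|---|---|---|---|
| Main effect power, 30 per arm | 77% | 65% | 56% |
| Interaction power, 30 per arm | 57% | 73% | 93% |
| Tests disagree, 30 per arm | 46.5% | 43.1% | 44.9% |
| Tests disagree, 40 per arm | 34.4% | 30.3% | 32.1% |

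Simulation agreed within its own error (43–48% and 31–34%).

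**4. One baseline-adjusted contrast, two-sided, 30 per arm.** SE² = (2/n)v, with v = (1 + 2ρ)/3 − ρ² for the average of three visits and v = 1 − ρ² for one visit. At ρ = 0.5 the average has SE = √(0.0667 × 0.417) = 0.167 and 0.65/0.167 = 3.9, giving 97%. One visit has SE = √(0.0667 × 0.75) = 0.224 and 0.65/0.224 = 2.9, giving 81%. The table includes the small loss from chance baseline imbalance.

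| | ρ = 0.3 | ρ = 0.5 | ρ = 0.7 |
|---|---|---|---|
| Average, constant effect | 96% | 97% | 99% |
| One visit, effect present there | 73% | 81% | 93% |
| Average, no effect at 6 months (mean effect 0.433) | 69% | 72% | 84% |
| Average, effect at 2 weeks only (mean effect 0.217) | 23% | 24% | 31% |
| One visit, effect gone by then | 5% | 5% | 5% |

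For comparison, the interaction has 70%, 85% and 98% when the effect is absent at 6 months, and 57%, 73% and 93% when it is present only at 2 weeks.

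**The case against.** The strongest reply is that the outcome is defined as change. With baseline as a level of time, a between-arm difference in change is the interaction, so the plan arguably points to that term. This narrows the choice without settling it. If change scores are the response, the same definition points to the arm effect, and the plan does not say which layout applies. The wording of the analysis sentence also keeps a between-group comparison in play.

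A reader might infer that the plan runs craving at a 9.75% error rate. The documents do not support that as fact. No rule says that either term suffices, and 9.75% applies only if either does. Named in advance, each term alone holds about 5%. What stands is that the rate is undetermined between 5% and about 9.75%.

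A reader might also take disagreement in nearly half of trials as the expected result. That range is for 30 per arm at every visit. The trial recruits 40 per arm, expects 80–85% retention at visit 24, and a mixed model uses earlier data from those who leave. With a constant effect the figure therefore lies between the two sample-size rows. It rests on assumed correlations and on baseline as a time level, and it rises if the effect fades.

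Finally, the error-rate problem would be cured by naming any single term, including the interaction, or by splitting alpha. The baseline-adjusted contrast is recommended because it estimates the one between-arm difference of interest; it is not the only valid remedy.

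**Conclusion.** The concern holds in conditional form. The plan names no deciding term, visit or baseline handling for the craving primary, and its correction does not reach the two arm-related tests. If either may be read as success, the false-positive rate on craving is about 9.75% instead of 5%; that figure depends little on the assumed correlations. With baseline as a time level and constant d = 0.65, the two tests disagree in about 43–47% of trials at 30 per arm and 30–34% at 40 per arm, which is illustrative because it depends on the assumptions listed. The point concerns the choice of term within CCQ; it does not count the second primary outcome or the choice between ANOVA and mixed model. It should be settled before unblinding.

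**What to change.** In the Statistical Analysis section, name one deciding test for CCQ before unblinding: the two-sided, 1-df active-minus-sham contrast from the linear mixed model already planned, with post-baseline CCQ as response and baseline CCQ as covariate. State whether it is taken at one visit or averaged over visits, and name them. Say that the ANOVA arm main effect and interaction are supportive only. Then restate the power calculation for that test, including its sidedness.

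The cost is wording; no new data or model is needed. There is a trade-off to record. The 96–99% power belongs only to the average under a constant effect. The average weakens if the effect fades, and then the interaction would usually have been the more powerful test. Naming one visit does not remove this risk: if the effect has gone by that visit, the test rejects only at its 5% level. The visit or visits should therefore be chosen with the stimulation-free last 12 weeks in mind.

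If the sponsor prefers to keep both ANOVA terms as tests of efficacy, run each at 0.025. The combined rate is then 1 − 0.975² = 4.94% under independence, and at most 5%.
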